## **Methods**

### **Study design**

The present study adopts quasi-experimental design. To avoid contamination between participants in two study arms, cluster sampling is used. Patients with T2DM of an endocrinology clinic in southern Taiwan are assigned to the intervention arm, whereas patients at another endocrinology clinic in southern Taiwan are placed in the control arm. Eligible patients that match the inclusion criteria are recommended by doctors to initiate insulin treatment after getting the consent forms from eligible participants. Research assistants will subsequently collect baseline data from eligible participants. Afterwards, the participants in the intervention arm will receive the intervention. For the control arm, the participants will receive regular patient education originally administered at the hospital. Data for the participants in both study arms will be collected by research assistants at baseline, 3 months, 6 months, and 12 months post-intervention. The main outcome variable is change in HbA1c levels, while the change in stage of change, in insulin injection adherence, in appraisal of insulin injection, in patient empowerment, in self-efficacy for insulin injection, in diabetes distress, in quality of life, in triglyceride(TG), in total cholesterol (TC), in high-density lipoprotein cholesterol(HDL-C), in low density lipoprotein cholesterol(LDL-C), in urine albumin creatinine ratio (UACR), in estimated glomerular filtration rate(GFR) are secondary outcome variables. The outcome

variables and collection time points are summarized in Table 1.

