## **Samples**

The inclusion criteria of eligible participants are: (1) diagnosed with T2DM for at least half a year; (2) aged 20-70 years old; (3) controlling diabetes only through oral medication, without previous experience in insulin injection; (4) HbA1c  $\geq 8.5\%$  as measured more than twice in the most recent year. Exclusion criteria were: (1) unable to communicate with language; (2) incapable of self-administering insulin injection due to visual or muscular impairment. Eligible participants who have been assessed and considered suitable for changing to insulin treatment by doctor will be included in this study.

Sample size estimation was done according to previous literature. An estimation of 63 participants in each study arm was calculated through setting a middle effect size of 0.5 between the two study arms in HbA1c levels,  $\alpha$  of 0.05, and power of 0.8. Furthermore, an attrition rate of 20% was expected. Therefore, each study arm should include at least 76 participants.

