### **Data Analysis**

The statistical software program SPSS 17.0 was used for data analysis. The Chi-squared test and independent t-test were used to compare differences in personal characteristics and outcome variables between the two groups before and after intervention. Paired t-tests were used to examine within-group differences at baseline, 3 months, 6 months, and 12 months post-intervention. A linear mixed-effect model that adjusted for the demographic data and baseline outcome variables was used to examine the changing amount of outcome variables from baseline to 3 months, to 6 months, and to 12 months post-intervention between the intervention and control arms. Participants were considered as a random effect. First-order autoregressive was used in the mixed-effect model analysis with the restricted maximum likelihood (REML) approach. A  $p$ -value  $< .05$  was considered statistically significant.

Table 1. Outcome measures and collection time points

Measures	Baseline	3 rd month	6 th month	12 th month
Demographic data & disease characteristics	✓	✓	✓	✓
Body mass index	✓	-	✓	✓
HbA1c	✓	✓	✓	✓
Lipids (TC, HDL-C, LDL-C, TG)	✓	✓	✓	✓
Renal function: UACR, GFR	✓	✓	✓	✓
Stage of change for insulin injection	✓	✓	✓	✓
Insulin injection adherence	-	✓	✓	✓
Appraisal of insulin injection	✓	✓	✓	✓
Empowerment	✓	-	✓	✓
Self-efficacy	-	✓	✓	✓
Diabetes distress	✓	-	✓	✓
Quality of life	✓	-	✓	✓

Table 2. Individual intervention plan

Stage of Change	Strategy	Process of Change
Precontemplation	
 
• Use examples in which good/bad glycemic control has a positive/negative impact on significant others to help patients reflect on their own HbA1c control
 
• Explain current health condition to patients through the changes in the curves of the their data
 
• Use UKPDS Risk Engine to predict the risk of cardiovascular disease and cerebrovascular event in the future 10 to 20 years in individual patients
 
	Consciousness raising

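### The main outcome, change in HbA1c, has no deciding visit or test: the trial is sized for one comparison at alpha 0.05, but between-arm change is examined at months 3, 6 and 12, each at p<.05

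*Combined protocol and SAP*

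**What the plan says.** All references are to the combined protocol and SAP.

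- **Study design**: "The main outcome variable is change in HbA1c levels". Data are collected "at baseline, 3 months, 6 months, and 12 months post-intervention", and no follow-up visit is singled out.
- **Samples**: the sample size comes from "setting a middle effect size of 0.5 between the two study arms in HbA1c levels", with alpha 0.05 and power 0.8, giving 63 per arm. No visit is attached to the effect size. The text continues: "an attrition rate of 20% was expected. Therefore, each study arm should include at least 76 participants".
- **Data Analysis**: a linear mixed-effect model, adjusted for demographic data and baseline outcome values, compares the arms on the "changing amount of outcome variables from baseline to 3 months, to 6 months, and to 12 months post-intervention". Independent t-tests also compare outcome variables between the groups, pre- and post-intervention, without saying which follow-up visit counts as post-intervention or whether level or change is tested. Paired t-tests cover within-group differences. A single general threshold applies: p < .05 "was considered statistically significant".
- **Table 1** ("Table 1. Outcome measures and collection time points"): HbA1c is ticked at baseline and at all three follow-up visits, and none is marked as primary.

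No section gives a deciding visit, a deciding test, a joint test over visits, a testing order or a multiplicity adjustment.

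**The concern.** The sample size and the analysis do not describe the same decision. The first has room for one comparison of the arms on HbA1c. The second produces at least three such comparisons from the mixed model, and possibly more from the t-tests, with nothing to say which one settles the question.

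Two things are at stake. If the visit that carries the claim can be chosen after the results are seen, the false-positive risk on the main outcome exceeds the nominal 5%. And a reader of the eventual report could not tell whether the highlighted visit, or the highlighted test, was fixed in advance.

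**Working it through.** **1. Reproduce the plan's size.** Inputs from Samples: standardised effect d = 0.5, alpha 0.05, power 0.8. Sidedness is not stated.

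n per arm = 2(z₁₋α/₂ + z_power)² / d² = 2(1.960 + 0.8416)² / 0.25 = 62.8, so 63. This matches. A one-sided test would give 50, so the plan's figure is that of one two-sided test. (The t-based version gives 64.)

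**2. Is there room for three comparisons?** With Bonferroni, alpha per visit = 0.05/3 = 0.0167 and z = 2.394:

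n per arm = 2(2.394 + 0.8416)² / 0.25 = 83.8, so 84. At 63 per arm, two-sample t power for d = 0.5 is 79.5% at alpha 0.05 and 64.8% at 0.05/3. The planned size therefore contains no allowance for three comparisons.

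**3. False-positive risk if any one visit counts.** Let Z₃, Z₆ and Z₁₂ be the three visit statistics under no effect, with a common correlation r. The risk is

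P(max|Z| > 1.96) = 1 − ∫ φ(u) [Φ((1.96 − √r·u)/√(1−r)) − Φ((−1.96 − √r·u)/√(1−r))]³ du.

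The documents give no correlations, so r is an assumption, shown over a range:

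| Assumed r | Any of three at p<.05 |
|---|---|
| 0.3 | 13.6% |
| 0.5 | 12.5% |
| 0.7 | 10.9% |
| 0.8 | 9.8% |
| 0.9 | 8.4% |

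If correlation instead decays with distance between visits (r, r, r²), simulation gives 12.9%, 11.4% and 8.8% at r = 0.5, 0.7 and 0.9. As a check with two-sample t contrasts at 61 per arm and equal correlation (100,000 null trials each), any-of-three gave 12.6%, 10.8% and 8.5% at r = 0.5, 0.7 and 0.9, against 4.9% to 5.1% for one visit fixed in advance. All these figures assume complete data, independent participants and no clinic effect, and none counts the t-tests as further routes to a claim.

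**4. Power if all three visits must be significant.** Alpha is then not inflated. Take the 61 per arm left after 20% loss from 76 (76 × 0.8 = 60.8), the same effect of 0.5 at each visit and the normal approximation. Each statistic has mean 0.5·√(61/2) = 2.76, and

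P(all three > 1.96) = ∫ φ(u) [1 − Φ((1.96 − 2.76 − √r·u)/√(1−r))]³ du,

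which is about 59%, 64% and 71% at r = 0.5, 0.7 and 0.9. With 63 per arm (mean 0.5·√(63/2) = 2.81) it is about 61%, 66% and 72%. Both sets fall short of the planned 80%.

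The power figures in steps 2 and 4 are for unadjusted comparisons, which is how the plan itself was sized. They are not the power of the adjusted mixed model.

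**The case against.** The strongest reply is that the plan nowhere says one significant visit means success. It describes one model covering three changes, and that could be meant as an overall comparison, or as requiring all three, neither of which inflates alpha. This stands as far as it goes: the inflation is conditional, and a reader who infers that the plan declares success on any visit goes further than the text. But the text does not rule that rule out, and the all-three reading does not deliver the planned power (step 4). The stated alpha and power both hold only if one comparison decides.

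Second, the correlations are assumed, and the relevant ones are those left after baseline adjustment. That is true. The range is not a bound, as the 13.6% at r = 0.3 shows.

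Third, 5% is a generous yardstick in this design. Arms are whole clinics and are not randomised: "patients at another endocrinology clinic in southern Taiwan are placed in the control arm". A clinic difference would add error that naming a visit does not touch. This stands, and it limits what the fix achieves, but it is no reason to leave the choice of visit open.

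Fourth, the mixed model already handles repeated measures. It does model within-person correlation, but it does not choose the contrast that decides. Nor can it safely be treated as the only between-arm comparison of change. Since the main outcome is itself a change, the independent t-tests can be read as a second one.

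**Conclusion.** The concern holds, and it should be fixed. The main outcome has no deciding visit and no deciding test, while the sample size is exactly that of one two-sided comparison at alpha 0.05. If any one visit could carry the claim, the risk from selection among visits would be about 12.5% to 8.4% for equal correlations of 0.5 to 0.9, and 13.6% at 0.3, instead of 5%. These figures rest on assumed correlations, an any-visit rule that the plan neither states nor excludes, and no clinic effect.

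Three stronger inferences are not supported. The documents do not show that the plan's error rate is 8% to 13%, because they state no success rule. They do not show that naming a visit brings the overall error to 5%, because arm and clinic coincide. And they do not show that the first-order autoregressive structure distorts the visit contrasts, because they give no variances or correlations from which to judge it. That choice is not part of this point.

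**What to change.** Before outcome data are analysed, add to Data Analysis:

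> The primary analysis is the between-arm difference in change in HbA1c from baseline to month [one named visit, for example 12], from the linear mixed model adjusted for the demographic data and baseline HbA1c as already planned, at two-sided alpha 0.05. Contrasts at the other visits and all t-tests are supportive.

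The documents favour no visit, so the choice is the sponsor's. The demographic adjustment should stay in the sentence: the comparison is not randomised, and leaving it out would open a new choice. A fixed testing order of the visits, each at 0.05 and stopping at the first non-significant one, is an acceptable alternative.

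The document is dated October 2017 and Data Analysis is written in the past tense, which does not settle whether analysis has been done. If outcome data have already been analysed, report all three visits and state that no primary visit was specified in advance.

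The cost is two sentences. The planned 63 evaluable per arm is unchanged, whereas a Bonferroni correction over three visits would need 84. The downside is that success can no longer be claimed on another visit alone; a fixed order keeps part of that option. The limits that come from having one clinic per arm remain and need to be acknowledged separately.

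### The mixed model's autoregressive covariance forces one variance on the 3-, 6- and 12-month visits, with no alternative planned, so visit-level tests are miscalibrated if the visit SDs differ

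*Combined protocol and SAP*

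**What the plan says.** Under Study design, data are collected "at baseline, 3 months, 6 months, and 12 months post-intervention", and "The main outcome variable is change in HbA1c levels". Table 1 confirms all four time points for HbA1c.

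Under Data Analysis, the adjusted between-arm comparison is "A linear mixed-effect model that adjusted for the demographic data and baseline outcome variables". It examines change "from baseline to 3 months, to 6 months, and to 12 months post-intervention between the intervention and control arms". The covariance is described in two sentences: "Participants were considered as a random effect" and "First-order autoregressive was used in the mixed-effect model analysis with the restricted maximum likelihood (REML) approach".

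The section does not say whether the autoregressive structure has equal or visit-specific variances, or whether baseline is also a repeated row. It gives no second structure, selection rule, robust standard error or sensitivity analysis.

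**The concern.** Ordinary first-order autoregression has one variance for all visits. A participant random intercept adds the same constant to every variance and covariance, so the variances remain equal. The fitted variance is then close to an average over visits, and each visit's standard error is built on that average instead of its own spread.

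The documents give reason to doubt constant spread. Entry requires HbA1c of at least 8.5%, which restricts the starting distribution. The follow-up responses on stage of change then run from having stopped insulin for good to injecting continuously for more than 6 months. This does not settle whether spread grows or shrinks, because control participants also have their treatment adjusted from self-monitoring results.

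At stake is the only adjusted between-arm analysis of the main outcome, in a non-randomised comparison of two clinics. The plan singles out no visit, so calibration matters at each one.

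**Working it through.** **Plan's own figure.** There is none to reproduce here. The sample-size paragraph gives only a standardised effect of 0.5, with no SD.

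**Inputs from the documents.** Post-baseline visits at 3, 6 and 12 months; random intercept plus first-order autoregression; comparison of arms at each visit; 5% significance level (two-sided assumed).

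**Assumed inputs.** Complete data, large sample, baseline as covariate, arm-by-visit terms. True correlation r over 3 months, between 0.6 and 0.8, decaying with time (r for 3–6, r² for 6–12, r³ for 3–12 months). Visit SDs as listed below.

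**Method.** Let S be the true 3×3 covariance and V the planned form, with entries σ_b² + σ²ρ^|i−j| on visit order. The large-sample fit minimises log|V| + tr(V⁻¹S). With complete data the estimated arm difference at visit j does not depend on V, so

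- model SE / true SE at visit j = √(V_jj / S_jj)
- type I error = 2[1 − Φ(1.96 × ratio)]

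**Step 1: unequal gaps only (equal SDs).** The ratio is 1.000 at every visit, so the error is 5.0%. Only between-visit contrasts move: for month 12 minus month 6 the ratio is 0.88–0.90 (SE 10–12% too small, error 7.7–8.4%).

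**Step 2: unequal SDs.** A hand check takes the common variance as the mean of the three variances:

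- 1.2/1.25/1.3: (1.44 + 1.5625 + 1.69)/3 = 1.564, root 1.251. Month 12: 1.251/1.3 = 0.962. Month 3: 1.251/1.2 = 1.042.
- 1.2/1.3/1.5: (1.44 + 1.69 + 2.25)/3 = 1.793, root 1.339. Month 12: 1.339/1.5 = 0.893. Month 3: 1.339/1.2 = 1.116.
- 1.2/1.4/1.8: (1.44 + 1.96 + 3.24)/3 = 2.213, root 1.488. Month 12: 1.488/1.8 = 0.827. Month 3: 1.488/1.2 = 1.240.
- 1.5/1.3/1.2: root 1.339 again. Month 12: 1.339/1.2 = 1.116. Month 3: 1.339/1.5 = 0.893.

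The full fit over r = 0.6–0.8 agrees closely:

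| Assumed SDs at 3/6/12 months | 3-month error | 12-month error |
|---|---|---|
| 1.2/1.25/1.3 | 4.1% | 5.9% |
| 1.2/1.3/1.5 | 2.8% | about 8% |
| 1.2/1.4/1.8 | 1.4–1.5% | 10.1–10.4% |
| 1.5/1.3/1.2 | about 8% | 2.8% |

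**Step 3: average over the three visits.** Its error stays at 4.6–5.0% in every scenario, because the excess at one visit offsets the deficit at another.

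**Step 4: attrition.** A separate simulation used 76 per arm, 20% completely random dropout, SDs 1/1.1/1.3, r = 0.7 and 600 trials (simulation error about 0.009). It fitted autoregression without the random intercept. The 12-month error was 0.108, against 0.063 with an unstructured covariance. With unequal gaps only, the two gave 0.063 and 0.065.

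**The case against.** **The spacing argument does not carry the point.** A reader might infer that treating a 3-month and a 6-month gap as the same lag invalidates the planned tests. The documents do not support that. The plan compares arms in change to each visit, where Step 1 shows no distortion if baseline is a covariate. The contrast that suffers, month 12 minus month 6, is not listed. If baseline were instead a repeated row, which the text leaves open, the gaps would mostly make standard errors too large: error 2.6–4.1% at 3 and 6 months and 5.0–5.6% at 12 months, for r between 0.5 and 0.85 and dropout of 0 or 20%. For BMI, empowerment, distress and quality of life there are only two post-baseline visits, so with baseline as covariate the gap question does not arise. This objection stands.

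**The SDs are not in the documents.** True, and the direction is unknown too. A reader might infer that the 12-month test is necessarily too liberal; the falling-SD scenario shows that it could equally be conservative. The 10% figure needs the variance to rise by a factor of (1.8/1.2)² = 2.25 between months 3 and 12. This limits the point to a conditional range.

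**A heterogeneous autoregressive form is not excluded.** Also true. If that was meant, the variance point falls away, but the text must say so.

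**Other analyses and larger problems exist.** The planned independent t-tests use each visit's own variance, but they are unadjusted. Assigning one clinic to each arm confounds arm with clinic, and no covariance option repairs that. It puts the present point in proportion without removing it.

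**Conclusion.** The point holds in a limited form. The plan commits to a structure that, read in the ordinary way, assumes equal variance at all post-baseline visits, and it provides nothing to fall back on. Under the assumed SDs, the nominal 5% test at a single visit could run from about 1.5% to about 10%. The mildest pattern examined moves the 12-month error only to 5.9%, and the three-visit average stays near 5% throughout. These figures rest on assumed SDs and correlations, complete data, a large sample and baseline as covariate. They show sensitivity and are not an estimate of the error in this trial. The case for acting is that the protection is cheap.

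**What to change.** In Data Analysis, replace the first-order autoregressive structure and the participant random intercept with an unstructured covariance over the post-baseline visits, with arm-by-visit terms. Enter the baseline value as a covariate where one is collected; Table 1 shows none for insulin adherence or self-efficacy, so the text should say how those two are modelled. If the model does not converge, use a heterogeneous-variance structure, named in advance.

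Dropping the random intercept loses nothing, since an unstructured covariance already contains it. It also removes a difficulty for the outcomes with two post-baseline visits, where a random intercept and autoregression cannot be separately identified.

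The cost is a change of wording and one model option. With three visits, an unstructured covariance has 6 parameters against 3 for the planned form, so 3 more, which about 76 participants per arm can support. If the variances prove equal, little is lost: in the gaps-only simulation the two structures had nearly the same error rates.

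### HbA1c and 13 secondary outcomes share one p < .05 rule, with no error control or supportive label for up to 36 secondary between-arm contrasts

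*Combined protocol and SAP*

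**What the plan says.** The Study design section names one main outcome, change in HbA1c. It then lists 13 further variables, ending "in urine albumin creatinine ratio (UACR), in estimated glomerular filtration rate(GFR) are secondary outcome variables". They are stage of change, injection adherence, appraisal of injection, empowerment, self-efficacy, diabetes distress, quality of life, TG, TC, HDL-C, LDL-C, UACR and GFR.

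The Data Analysis section applies a linear mixed model to the outcome variables in general and compares their change "from baseline to 3 months, to 6 months, and to 12 months post-intervention between the intervention and control arms". It adds chi-squared and independent t-tests between groups, and paired t-tests within groups. One sentence then covers all of these analyses: a p-value below .05 "was considered statistically significant".

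The Samples section sizes the trial on HbA1c alone, "setting a middle effect size of 0.5 between the two study arms in HbA1c levels", with α "of 0.05, and power of 0.8". Nowhere do the documents adjust for the number of secondary outcomes, set an order among them, or call them supportive or exploratory.

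**The concern.** The plan separates main from secondary outcomes when it names them, but the analysis section makes no use of the distinction. A secondary result at any visit earns the same label as the HbA1c result if its p-value is below .05. With this many contrasts, some can be expected to cross that line when nothing is happening.

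What is at stake is the reading of the secondary results. Seven of the 13 are self-reported, and allocation is by clinic without randomisation. The study's aim is to assess effectiveness. Nothing in the plan would prevent an isolated p-value below .05, on one scale at one visit, from being reported as an effect. The point does not touch the HbA1c test, nor which visit should decide it.

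**Working it through.** **1. The plan's own figure.** The documents state no family-wise error rate. The only calculation that uses α is the sample size. With a standardised effect of 0.5, two-sided α 0.05 (sidedness assumed) and power 0.8, the normal approximation gives n = 2 × (1.960 + 0.842)² / 0.5² = 62.8. This rounds up to 63 and matches "An estimation of 63 participants in each study arm". So the 5% level was budgeted for one comparison, HbA1c.

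**2. Count of secondary between-arm contrasts, from Table 1.**
- Ten outcomes have follow-up at months 3, 6 and 12: 10 × 3 = 30.
- Three outcomes (empowerment, distress, quality of life) have no month-3 measurement: 3 × 2 = 6.
- Total: 36.
- Adherence and self-efficacy have no baseline, so no change from baseline can be formed for them. Without these two: 36 − 6 = 30.
- Leaving out stage of change as well (categorical, with different questions at baseline and follow-up): 30 − 3 = 27.

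The additional t-tests, chi-squared tests and within-group tests are not counted.

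**3. Independent tests, every null true, each test at 5%.** P(at least one false positive) = 1 − 0.95^k; expected number = 0.05k.

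| k | Basis | Expected number | P(at least one) |
|---|---|---|---|
| 36 | all contrasts | 1.8 | 84.2% |
| 30 | without adherence and self-efficacy | 1.5 | 78.5% |
| 27 | also without stage of change | 1.35 | 75.0% |
| 13 | one visit (month 6 or 12), or one overall test per outcome | 0.65 | 48.7% |

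**4. Correlated tests.** The documents give no correlations, so a range is assumed. Correlated two-sided z-tests were simulated on the Table 1 schedule, with one common correlation between outcomes and one between visits.

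| Between outcomes | Between visits | P(any of 36) | P(any of 13, month 12) |
|---|---|---|---|
| 0 | 0.6 | 78% | 49% |
| 0.3 | 0.6 | 71% | 42% |
| 0.5 | 0.7 | 58% | 33% |
| 0.6 | 0.8 | 47% | 29% |
| 0.7 | 0.7 | 44% | 24% |

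If the correlation between visits instead decays with their spacing (first-order autoregressive), the 36-contrast figures rise by about one to two points, and the last two rows stay below 50%. With 30 contrasts, correlations of 0.5 and 0.7 give about 53%.

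**5. A condition on all these figures.** They assume that each test has a true 5% error rate. The Study design section assigns one clinic to each arm, so differences between clinics cannot be separated from the intervention. The real rate of spurious differences may therefore not be 5% even for a single test.

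**The case against.** A reader might infer that the plan declares all 13 outcomes significant at every visit, or that a false secondary effect is more likely than not whatever is assumed. The documents support neither. The outcomes are tested against .05, not declared significant, and three are not measured at month 3. The chance of a false positive exceeds one half only when contrasts are counted across visits and correlation is low to moderate. At one visit, or with one overall test per outcome, it is below one half even under independence.

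It can also be argued that naming one main outcome and powering on it is already a two-level ranking, and that formal error control for secondary outcomes is partly convention. That is fair as far as it goes: the trial has one main claim, and no success rule rests on a secondary outcome. That secondary results would be promoted if HbA1c were neutral is a risk, not something the plan states. But the convention relies on secondary results being presented as supportive, and here the analysis section gives them the same significance label as the main outcome.

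The count of 36 is an interpretation, since two outcomes lack a baseline and stage of change does not fit a linear change model cleanly. These outcomes could still be compared by the other between-group tests, so 36 is an upper count for one between-arm test per outcome and visit. The 30- and 27-contrast figures lead to the same conclusion.

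Finally, no multiplicity method removes clinic confounding. That stands. It is a reason to prefer estimation and labelling to a corrected threshold.

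**Conclusion.** The point holds as a gap in labelling and error control for the secondary outcomes. Across up to 36 contrasts, the chance of at least one false positive is 84% if the tests are independent, about 58–78% under low to moderate correlation, and about 44–47% under strong correlation. With 13 tests at one visit it is about 29–49% for between-outcome correlations from 0.6 down to 0, and lower if correlation is stronger. These figures rest on all nulls being true, on each test holding 5%, and on assumed correlations. The one-clinic-per-arm design makes the second condition doubtful. Only secondary claims are affected.

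**What to change.** In the Data Analysis section, limit the p < .05 significance rule to the main outcome, change in HbA1c. State that the secondary outcomes will be reported as adjusted between-arm differences with 95% confidence intervals, labelled supportive, with no significance claims.

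If the sponsor wants a claim on a secondary outcome, the plan should name in advance the multiplicity procedure and the visit to which it applies. The documents designate no deciding visit, so that choice is the sponsor's. Such a procedure would not address clinic confounding.

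The cost is two sentences, with no new data, participants or procedures. The downside is that fewer secondary results can be called significant.
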